## 6 STUDY INTERVENTION(S) OR EXPERIMENTAL MANIPULATION(S)

### 6.1 ENDPOINT

The primary outcome will be change in behavioral intent to call 911. It will be measured using a 16 item assessment, of which 4 are non-stroke distractors, based on a previous assessment used in the Flint community as well as a larger sample in Michigan (HUM00036399 and HUM0006687).

**Secondary outcomes:** The tertiary/exploratory outcomes include change in stroke recognition based on the BRFSS, stroke self-efficacy, outcome expectations and social norms based on questions used in a previous intervention in this community.

### STATISTICAL CONSIDERATIONS

### 6.2 STATISTICAL HYPOTHESES

#### 6.2.1 ANALYSIS OF ENDPOINT(S)

The primary analysis will fit a linear regression model with the outcome of change in behavioral intent to call 911 (post minus pre) and main effect-coded binary predictor intervention group. Results will be reported as parameter estimates, 95% confidence intervals, or as the average

marginal effects and 2-sided p-values. We anticipate the tertiary/exploratory variables will be analyzed using the same strategy, although logistic regression models may be used depending on the properties of the collected data.

Previous studies note a 6 point improvement (sd=6) in behavioral intent to call 911 based on (21 stroke vignettes) after a 15 minute video intervention. There was no control group and thus we cannot assess the test and re-test properties of their measure. Given our measurement instrument is fewer questions and has higher baseline estimates than the previously used estimate, STAT, that the sample size calculations are based off of, we anticipate less improvement. We estimate a 3 point improvement in the intervention group and a 2 point improvement in the control group (test-re-test). Thus with sd (2), power 80, alpha 0.05, we plan to enroll 63 subjects in each arm.

The table below is intended to capture changes of IRB-approved versions of the protocol, including a description of the change and rationale. A **Summary of Changes** table for the current amendment is located in the **Protocol Title Page**.

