### Brief Intervention

Peer leaders will deliver the brief stroke preparedness intervention.

These core components include, and are defined as follows:

1. **What is Stroke:** defines what a stroke is and what causes it.
2. **Stroke Happens :** facts about incidence and prevalence of stroke, as well as defining the consequences of stroke.
3. **Stroke Signs (FAST):** Review of signs of stroke—face drooping, arm weakness, speech difficulties, and time to call 911, as well as how to check for each sign.
4. **Stroke is treatable. TPA—the clot blaster:** visual demonstration and/or illustration showing what happens during a stroke and how TPA works to remove a blockage in the brain.
5. **Time is everything:** explanation that medicine to treat stroke can only be given in the hospital, and that earlier treatment is given, the better the chance of recovery.
6. **Stroke Ready Action Plan:** a step-by-step plan to guide a person through calling 911 if they see signs of stroke, and a reminder of the steps to follow when doing so.

The healthy behavior intervention consists of patient materials from the American Heart Association.

The intervention will be conducted by members of the research team in space provided by the community clinics and senior center, similar to our previous procedures (HUM00084543, HUM00145724). The interaction (pre-test—intervention—post-test) will take about 30 minutes. We will provide the subjects \$20 in cash in appreciation of their time. Identifiers will not be collected and thus we will not collect identifiers of subjects who are paid for their participation.

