### 5.3 STRATEGIES FOR RECRUITMENT AND RETENTION

Subjects will be recruited from Hamilton Community Health Center and Senior Centers. We have recruited from both of these venues in the past (HUM00093846, HUM00145724). The subjects will be invited to participate when asked by a team member or member of the clinic medical staff. Subjects from the senior center will be recruited during center events. Recruitment announcements, flyers, internet platforms, and word-of-mouth may also be used.

There is no retention. Subject identifiers are not collected and subjects are not contacted after initial interaction.

Subject agreement will be sought at the start of the interaction by members of the research team. Any subject who declines will be thanked for their participation and the interaction will cease. A copy of the agreement form will be provided to subjects.

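### The primary model regresses change on group alone; adding the pre-test score, which is already collected, would gain precision at almost no cost

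*Combined protocol and SAP*

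**What the plan says.** Section 6.1 defines the endpoint: "The primary outcome will be change in behavioral intent to call 911". Section 6.2.1 models "change in behavioral intent to call 911 (post minus pre) and main effect-coded binary predictor intervention group". Group is the only predictor named, and no other section adds the pre-test score or any other covariate.

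The pre-test is part of the design. Table 1 in Section 3 gives the timing of the primary outcome as pre and post, and the Brief Intervention text in Section 4.1 says: "The interaction (pre-test—intervention—post-test) will take about 30 minutes".

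The sample-size paragraph in Section 6.2.1 assumes: "We estimate a 3 point improvement in the intervention group and a 2 point improvement in the control group (test-re-test"). It continues: "Thus with sd (2), power 80, alpha 0.05, we plan to enroll 63 subjects in each arm". The same paragraph explains why less improvement is expected than in an earlier study: "Given our measurement instrument is fewer questions and has higher baseline estimates than the previously used estimate". It gives no baseline mean, scale maximum or pre-post correlation.

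For the other outcomes: "We anticipate the tertiary/exploratory variables will be analyzed using the same strategy", with logistic regression left open as an alternative.

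**The concern.** Regressing change on group alone fixes the slope of post-test on pre-test at 1. At any other slope, part of the variation in change is predictable from the pre-test score, and the planned model leaves it in the residual. Entering the pre-test score estimates the slope instead. The group coefficient still targets the difference in mean change, and it is identical whether the outcome is entered as post-test or as change.

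At stake is the precision of the primary estimate. The same loss can be seen another way: in any one realized trial the unadjusted estimate moves with chance baseline differences between the arms. These are two descriptions of one loss and should not be added together.

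A slope below 1 is likely, because of regression to the mean and because the plan expects high baseline scores to limit improvement. The documents do not establish it.

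**Working it through.** **Inputs from Section 6.2.1:** difference in mean change 3 − 2 = 1; SD 2; two-sided alpha 0.05; power 80%; 63 per arm.

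**Assumptions, because the documents are silent:** pre-post correlation r between 0.3 and 0.9; equal pre and post variances, relaxed in step 4.

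**1. The plan's own figure.** n per arm = 2 × (1.96 + 0.8416)² × 2² / 1² = 62.8, so 63. It reproduces. The SE is 2 × √(2/63) = 0.356 and the 95% CI half-width is 0.71. Power is 80.1% by the normal approximation and 79.5% by the noncentral t (124 df). The noncentral t is used below.

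**2. Adjusted model, SD 2 read as the SD of change.** With equal variances, the residual variance of the adjusted model divided by the variance of change is (1 + r)/2. The residual SD is therefore 2 × √((1 + r)/2), with 123 df.

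| r | variance ratio | residual SD | SE | power | power allowing for chance imbalance |
|---|---|---|---|---|---|
| unadjusted | 1 | 2.000 | 0.356 | 79.5% | – |
| 0.3 | 0.65 | 1.612 | 0.287 | 93.2% | 93.0% |
| 0.5 | 0.75 | 1.732 | 0.309 | 89.5% | 89.3% |
| 0.7 | 0.85 | 1.844 | 0.329 | 85.5% | 85.3% |
| 0.8 | 0.90 | 1.897 | 0.338 | 83.5% | 83.2% |
| 0.9 | 0.95 | 1.949 | 0.347 | 81.5% | 81.2% |

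The last column adds about 0.8% to the variance for the expected chance difference in baseline. The 95% CI half-width falls from 0.71 to 0.57 at r = 0.3 and to 0.69 at r = 0.9.

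**3. Simulation** (20,000 trials per setting, normal scores, no ceiling). The mean estimate was 1.00 and type I error about 5% under both models. Power for change versus adjusted was 79.8% vs 92.8% (r = 0.3), 79.6% vs 89.6% (0.5), 79.3% vs 84.9% (0.7) and 79.4% vs 81.3% (0.9).

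**4. Unequal variances.** What matters is how far the slope, r × SD(post)/SD(pre), lies from 1. With the SD of change held at 2 and chance imbalance included:

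| SD(post)/SD(pre) | r | slope | adjusted power |
|---|---|---|---|
| 1.25 | 0.8 | 1.00 | 79.2% |
| 1.1 | 0.9 | 0.99 | 79.2% |
| 1.25 | 0.7 | 0.875 | 80.0% |
| 0.8 | 0.8 | 0.64 | 93.4% |

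The worst case is a slope of 1, which costs 79.5 − 79.2 = 0.3 points. A ceiling that compresses post-test scores would enlarge the gain.

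**5. The other reading of SD 2.** If 2 is the SD of a single score, the SD of change is 2 × √(2(1 − r)) and the adjusted residual SD is 2 × √(1 − r²). Power without and with adjustment is then 65.3% vs 83.1% (r = 0.3), 79.5% vs 89.5% (0.5), 94.9% vs 97.4% (0.7) and 99.3% vs 99.6% (0.8).

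**6. Sensitivity to baseline imbalance.** With the SD of change equal to 2, the SD of a score is σ = 2/√(2(1 − r)). A baseline difference of one standard error shifts the unadjusted estimate by (1 − r) × σ × √(2/63). That is 0.21 (r = 0.3), 0.18 (0.5), 0.14 (0.7) or 0.08 (0.9) points, against a planned effect of 1.

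**The case against.** The strongest reply is that nothing is wrong with the plan. The endpoint is change, the model analyses change and the sample size is computed for change, so all three agree. What remains is a choice between two valid estimators, and the benefit of switching depends on quantities the documents do not give. With pre-test and post-test in one session of about 30 minutes, r may well be high, and at 0.8 to 0.9 the gain is only 2 to 4 points. With unequal variances it can vanish. All of this stands. It bears on the size of the gain and not on its direction: the possible loss is about 0.3 points, the possible gain more than 13.

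Three further objections stand in part:

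- SD 2 is most naturally the SD of change, since the only other SD in that paragraph belongs to an improvement. The 65.3% figure comes from the less natural reading, and the conclusion does not rest on it.
- Adjustment is not literally free: it costs one degree of freedom and about 0.8% in expected variance.
- For an exploratory outcome analysed by logistic regression, adding a covariate changes what the odds ratio estimates, so extending the adjustment there requires average marginal effects, which Section 6.2.1 mentions only as an option.

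Scores near the top of the scale could make the pre-post relation non-linear. Randomization keeps the adjusted estimate valid in that case, and robust standard errors would be a sensible addition.

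**Conclusion.** The concern holds as an efficiency improvement to the primary analysis, not as an error. The planned estimator is unbiased and the sample size is reproducible. Under the assumptions of equal variances, SD of change 2, true difference 1 and 63 per arm, adjustment adds between 2 points of power (r = 0.9) and 13.7 points (r = 0.3). If the slope is about 1, it gives up about 0.3 points. The documents do not say where r lies, so the gain could be anywhere from nil to substantial. Because the cost is close to zero and the primary result is affected, the change should be made.

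**What to change.** In Section 6.2.1, state the primary analysis as a linear regression of the post-test intent score (or, equivalently for the group effect, of change) on randomized group, with the pre-test intent score as a covariate. Report the adjusted mean difference, its 95% CI and the two-sided p-value. Keep the unadjusted change model as a sensitivity analysis. Fix the choice before outcome data are seen, so that it cannot look like model selection.

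Apply the same adjustment to exploratory scores that have a pre-test and are analysed linearly; where a logistic model is used, report average marginal effects. In the sample-size paragraph, say whether SD 2 is the SD of change or of the score.

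The cost is a few sentences of text and one degree of freedom. It needs no new data and no extra participants, and it drops nobody whom the change score would keep, since a missing pre-test already leaves change undefined.

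### Does effect coding of the group variable mean the primary result will be reported at half its true size?

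*Combined protocol and SAP*

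**What the plan says.** The primary analysis in section 6.2.1 is a "linear regression model with the outcome of change in behavioral intent to call 911 (post minus pre"). Its only predictor and the first reporting scale are described together: "main effect-coded binary predictor intervention group. Results will be reported as parameter estimates, 95% confidence intervals". No numeric codes are given for the two arms.

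The second reporting scale, offered as an alternative, is the average "marginal effects and 2-sided p-values". The section does not say which scale is primary. It also does not say in so many words that the reported figure is intervention minus control.

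The sample size paragraph in the same section works with the difference between arms: "We estimate a 3 point improvement in the intervention group and a 2 point improvement in the control group (test-re-test"), followed by "Thus with sd (2), power 80, alpha 0.05, we plan to enroll 63 subjects in each arm".

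**The concern.** In a regression with one binary predictor coded -1 and +1, the coefficient is the distance of either arm from the midpoint of the two arm means. That is half the difference between arms. A plan that calls the predictor effect-coded and lists the parameter estimate with its confidence interval as a way to report the result could therefore print an effect and interval at half the scale used to size the trial.

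The p-value would give no warning, because it does not depend on the coding. A reader who set the printed coefficient beside the planned 1-point difference would think the effect smaller than it was. The two reporting options could also differ by a factor of two on the same data. The model has no interaction term, so effect coding has no evident advantage over a 0/1 indicator.

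**Working it through.** **Inputs, all from section 6.2.1:** mean change 3 (intervention) and 2 (control), SD 2, 63 per arm, alpha 0.05, power 80%. The p-values are stated to be two-sided.

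**1. Reproduce the sample size.** With the usual normal approximation:

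n per arm = 2 × (1.960 + 0.842)² × SD² / difference² = 2 × 7.85 × 4 / 1² = 62.8, rounded up to 63.

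This matches the plan, and power at 63 per arm is 80.1%. The design quantity is therefore the full 1-point difference between arms.

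**2. Standard error and interval for that difference.**

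- SE = 2 × √(2/63) = 0.356
- t = 1.00 / 0.356 = 2.806 on 124 degrees of freedom, p = 0.0058
- 95% half-width = 1.979 × 0.356 = 0.705, giving 0.295 to 1.705

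**3. The same model under three codings.** Ordinary least squares was fitted to data constructed to have exactly these means and SDs:

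| Codes (control / intervention) | Intercept | Group coefficient | SE | 95% CI | t | p |
|---|---|---|---|---|---|---|
| 0 / 1 | 2.0 | 1.00 | 0.356 | 0.295 to 1.705 | 2.806 | 0.0058 |
| -1 / +1 | 2.5 | 0.50 | 0.178 | 0.147 to 0.853 | 2.806 | 0.0058 |
| -0.5 / +0.5 | 2.5 | 1.00 | 0.356 | 0.295 to 1.705 | 2.806 | 0.0058 |

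Only the -1/+1 row is halved. Coefficient and standard error shrink together, so t, p and power do not change, nor does whether the interval excludes zero.

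**4. The marginal-effect option under -1/+1 codes.**

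- Contrast between arms: predicted change is 2.5 + 0.5 = 3.0 for intervention and 2.5 - 0.5 = 2.0 for control. The difference is 1.0, the full effect.
- Slope per unit of the numeric code: 0.50, half the effect. This arises only if the software is told to treat group as a continuous variable.

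**5. What a misleading report would require.** Three things must happen together: the codes are -1/+1; the raw coefficient (or a per-unit slope) is chosen over the contrast between arms; and it is published without the coding or the arm means. If the coding or the arm means are shown, the reader can recover the difference by doubling or by subtraction.

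**The case for a change.** The best argument for a change is that the ambiguity is real and would cost one sentence to remove. If the trial observed exactly its planned 1-point effect and printed the -1/+1 coefficient, the upper confidence limit would be 0.853. A reader might conclude that the planned effect had been excluded when it was in fact the observed value. The offer of marginal effects does not close the gap, because it is only an alternative. The exploratory outcomes follow the same strategy, possibly with logistic regression. There, exponentiating a -1/+1 coefficient gives the square root of the odds ratio between arms, so an odds ratio of 4 would print as 2.

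This arithmetic is right, and section 6.2.1 does leave both the codes and the primary scale unstated. But the argument depends on codes that the plan does not give, and another form of effect coding has no such consequence. The wording can even be read as a main effect for a coded binary predictor, with no effect coding in the technical sense. The 1-point figure is a planning value: the documents name no minimum important difference and no success criterion on that scale. A -1/+1 coefficient is a correct number on a known scale, and becomes misleading only if reported without that scale. What stands is that a sentence naming the contrast would be tidier.

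**Conclusion.** No change to the plan follows. Under one of the possible codings and one of the possible reporting choices, the printed estimate and interval would be half the difference between arms: 0.50 in place of 1.00 at the planning values, with a half-width of 0.35 in place of 0.71. Under 0/1 or -0.5/+0.5 coding, or with a marginal effect taken as the contrast between arms, the full difference is reported. The hypothesis test, type I error, power and 63 per arm are identical in every case.

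This is a missing detail that analysts fill sensibly. A two-arm trial sized on a difference in mean change will ordinarily present that difference, and the plan's marginal-effect option already points that way. The conclusion assumes that the report will give the contrast between arms, or else state the coding or the arm means. Writing the codes down in advance would alter neither the analysis nor any conclusion drawn from it.

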## 3 OBJECTIVES AND ENDPOINTS

Table 1: Stroke Preparedness Brief Intervention Outcomes		
Primary Outcome		
Intervention Goal	Outcome Measure	Timing
Increase behavioral intent to call 911	STAT	Pre-post
Secondary Outcome		
Increase stroke recognition	Survey	Pre-post
Improve self-efficacy, attitude, social norms	Self-efficacy, Attitude, subjective norm	Pre-post
Satisfaction		Post

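### Does the unsourced SD of 2 behind 63 per arm call for a change to the sample size or the plan?

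*Combined protocol and SAP*

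**What the plan says.** Section 6.2.1 of the combined protocol and SAP starts from earlier work: "Previous studies note a 6 point improvement (sd=6) in behavioral intent to call 911 based on (21 stroke vignettes". It notes that this work had no control group, so practice effects from repeating the test cannot be separated out. It then explains why the trial should expect smaller gains: "Given our measurement instrument is fewer questions and has higher baseline estimates than the previously used estimate", and so "we anticipate less improvement". The gains follow: "We estimate a 3 point improvement in the intervention group and a 2 point improvement in the control group (test-re-test". The last step is "Thus with sd (2), power 80, alpha 0.05, we plan to enroll 63 subjects in each arm". No citation or reason is attached to the SD.

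The primary analysis in the same section is a linear regression of the change score (post minus pre) on randomized group, with two-sided p-values.

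Section 6.1 describes the primary measure as follows: "16 item assessment, of which 4 are non-stroke distractors". On where this measure comes from, the section says that it is "based on a previous assessment used in the Flint community as well as a larger sample in Michigan". It reports no SD from those earlier uses. Table 1 in section 3 labels the same outcome differently: "Increase behavioral intent to call 911 STAT Pre-post".

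**The concern.** The SD is the only variance input behind 63 per arm. The one SD the plan cites is three times larger. The expected gain is halved, from 6 points to 3, and a reason is given; the SD is cut to a third, and none is. Fewer questions would explain only part of that fall on a simple rescaling. It is then natural to suspect that 2 was chosen because it gives a convenient sample size.

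It can also seem that the plan contradicts itself. In SD units the cited gain is 6/6 = 1.0 and the planned intervention gain is 3/2 = 1.5, which looks like more improvement where the text expects less.

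At stake is power. If the true change-score SD were well above 2, a trial of 126 people could miss a real 1-point effect, and a null result would say little. The STAT label in Table 1 adds some doubt about which instrument the SD belongs to.

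**Working it through.** **Inputs (section 6.2.1).** Gains 3 and 2, so difference d = 1 point; SD s = 2; alpha 0.05, taken as two-sided because the analysis reports two-sided p-values; power 80%; equal arms. Reading s as the SD of the change score is an inference. It fits the change-score outcome, and it reproduces the plan's figure.

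**Reproducing 63.** Normal approximation:

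n per arm = 2 × (1.960 + 0.842)² × s² / d² = 2 × 7.851 × 4 / 1 = 62.8, rounded up to 63.

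The t-based version gives 64 per arm, and 79.5% power at 63. The difference is immaterial.

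**Sensitivity to the SD.** Two-sided 0.05, 1-point difference, noncentral t. Every SD except 2 and 6 is an assumption.

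| Change-score SD | Power at 63 per arm | Difference detectable at 80% | n per arm for 80% |
|---|---|---|---|
| 1.5 | 96.0% | 0.76 | 37 |
| 1.75 | 88.9% | 0.88 | 50 |
| 2 (plan) | 79.5% | 1.01 | 64 |
| 2.5 | 60.6% | 1.26 | 100 |
| 3 | 45.9% | 1.51 | 143 |
| 3.43 | 36.9% | 1.72 | 186 |
| 6 (cited, other instrument) | 15.3% | 3.02 | 567 |

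The columns show how power responds to the SD in any trial of 63 per arm aimed at half an SD. They do not show which row applies here.

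**Can the SD be carried over from the cited study?** The trial's instrument has 16 − 4 = 12 stroke items against 21. If both score one point per item (assumption; the text available gives no scoring rule for either), proportional scaling gives 6 × 12/21 = 3.43. If instead item changes were independent, the scaling would be 6 × √(12/21) = 4.54. Both exceed 2, so item count alone does not reach the plan's value. But neither allows for the higher baseline. People who already score near the top have little room to change, which lowers the spread as well as the mean of the change. The documents give no figure for that effect, so these rescalings cannot show that 2 is too small.

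**Does the gain-to-SD comparison matter?** No. The primary model compares change between arms, so power depends on (3 − 2)/2 = 0.5. Adding the same constant to both gains alters the ratios 1.5 and 1.0 but leaves n at 63. The cited 6/6 = 1.0 is an uncontrolled before-after gain, so it supplies no between-arm effect to compare with 0.5. The expectation of less improvement is about points, and 3 is less than 6.

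**Does the planning SD enter the analysis?** No. The regression estimates the residual variance from the trial's own data. The planning value of 2 appears nowhere in the estimate, interval or test.

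**Which instrument?** Section 6.1 defines the 16-item assessment. Section 6.2.1 contrasts the trial's own shorter instrument with STAT, the measure behind the cited figures. The Table 1 cell is the odd one out.

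**The case for a change.** The best case for acting is that the plan itself says its calculation rests on the cited study, cites one SD from it, and then uses another that is a third as large. A reader cannot judge a null result against the design without knowing where 2 came from: an SD of 2.5 instead of 2 would take power from about 80% to 61%. The remedy would be cheap, a sentence or two in section 6.2.1 and one cell of Table 1.

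The factual part of this stands. The source is not stated, the two reasons given are attached only to the size of the gain, and a note that 2 is an assumption would have been good practice. What does not follow is that the design is faulty. The case grants that 2 has not been shown to be wrong, and it proposes no other value. Section 6.1 says the parent assessment had already been used in Flint and more widely in Michigan, so the investigators may have had data behind the figure; whether they did cannot be told from the documents. A sentence naming the source would leave enrolment, procedures and analysis as they are. After the trial, the width of the observed confidence interval tells the reader directly what a null result excludes.

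**Conclusion.** No change to the plan is needed. The figure of 63 per arm is correct for a 1-point difference, SD 2, two-sided 0.05 and 80% power (62.8 before rounding). The missing source for the SD is a gap in explanation. It could matter for power, which runs from 96% to 46% over assumed SDs of 1.5 to 3 and would be lower still above 3, but the documents contain nothing that places the true value away from 2. The apparent conflict in SD units disappears once the between-arm ratio of 0.5 is used. The STAT entry in Table 1 is a clerical slip that sections 6.1 and 6.2.1 together resolve.

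This rests on two readings: that the stated SD is that of the change score, which reproducing 63 supports, and that the primary regression uses the variance observed in the trial, as ordinary linear regression does. The conclusion is not that 2 is right. It is that nothing in the documents shows it to be wrong, and that stating its source would change no result.
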